No formal sample size calculation is being conducted for the follow-up study. A maximum of two hundred and one (201) participants will be recruited from PPOIT-003 trial (PPOIT n=79; OIT n=83; placebo n=39).

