4. VARIABLES

4.1. OUTCOMES

Table 1 –Outcomes description

	Outcome	Description
А	Peanut ingestion (intentional or accidental)	Binary outcome
	between T1 and F1	
		1=Yes if ingested peanut at least once over
		the 12 months period.
		0=No
В	Reaction to peanut ingestion (intentional or	Binary outcome
	accidental) between T1 and F1	1=Yes if reacted to peanut at least once
		over the 12 months period
		0=No
С	Number of reactions to peanut ingestion	Continuous outcome
	(intentional or accidental) T1 and F1 overall	
	and by severity	and Categorical outcome
		1=1 reaction
		2=2 reactions
		3=3 or more reactions
D	Use of EpiPen to treat reaction to peanut	Binary outcome
	(intentional or accidental) between T1 and F1	1=Yes if used EpiPen to treat reaction to
	(peanut at least once over the 12 months
		period
		0=No
E	Number of times using EpiPen to treat	Continuous outcome
-	reactions to peanut (intentional or accidental)	
	between T1 and F1	
F	Weekly average quantity of peanut protein	Continuous outcome
	ingested (intentional or accidental) between	
	F0 and F1	and Categorical outcome
		1=Never ingested
		2=Minimal amount (less than 1 peanut,
		<250g)
		3=Small amount (1-2 peanuts, 250-599g)
		4=Moderate amount (3-8 peanuts, 600-
		1999g)
		5=Large amount (>2000g)
G	Weekly average frequency of peanut	Continuous outcome
	ingestion (intentional or accidental) between	
	F0 and F1	and Categorical outcome
		1=Nil
		2=Less than once a month
		3=Once a month to <1/week
		4=1-2 times/week
		5=3-5 times/week
		6=>5 times a week
н	Quality of life scores – total, sub-scores	Continuous outcome. From FAQLQ-PF, tot
	(emotional impact, food anxiety, social and	score is calculated as the mean of up to 30
	dietary limitations) and FAIM total score at F1	items (some are age specific), with
		response scale from 0 (minimal impairmer
		in QoL) to 6 (maximal impairment in QoL).

		The mean scores for selected items are used to construct the sub-scores. The FAIM consists of 4 questions, scored on a 7-point scale. The FAIM total score is the mean of all items and ranges from 0 (limited severity perception) to 6 (greatest severity perception).
I	Change in quality of life scores (total, sub- scores, and FAIM) from screening in PPOIT- 003 study to F1	Continuous outcome

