For continuous outcomes, the mean difference between treatment groups will be obtained by using GLM to account for clustering by site, adjusted by the age group at randomisation (1-5 years; 6-10 years) and SPT wheal size (\leq 10mm; >10mm). The median difference using quantile regression model to adjust for the stratification factors if not normally distributed.

We will also compare the QoL scores using a mixed model applied to the data at 4 timepoints (T0, T1, T3/F0, F1) and account for clustering by study site, with fixed effects for treatment, age group at randomisation and SPT wheal size, and a random effect to allow for repeated measures for each individual.

ESTIMATION OF EFFECTS (BETWEEN CLINICAL OUTCOME GROUPS)

For binary outcomes, a binary regression model will be used.

For continuous outcomes, the mean difference between the clinical outcome groups will be obtained by using linear regression. Adjusted linear regression will be used to adjust for baseline QoL score in outcome I. The median difference using quantile regression model if not normally distributed.

HANDLING OF MISSING DATA

It is anticipated that 25% of children will not continue to participate the follow-up, due to participant attrition and parent/guardian non-response. The available case analysis will be the

(FORM: SAP template interim analysis/Version 1.1)

primary one. A sensitivity analysis using Inverse Probability Weighting (IPW) and Multiple Imputation (MI) techniques will be used to handle the missing data (details in section below).

SENSITIVITY ANALYSIS

The sensitivity analysis will be performed on an intention-to-treat basis including all the children whose parent/guardian consented for follow-up, with IPW and MI techniques used to handle the missing data. It is anticipated that 25% of the original sample of 201 children will have follow-up outcomes missing. In such situations, we will use both MI combined with IPW techniques (Seaman, S.R., White, I.R., Copas, A.J. and Li, L., 2012. Combining multiple imputation and inverse-probability weighting. Biometrics, 68(1), pp.129-137.) as a sensitivity analysis. It involves two major steps:

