5.2. F1 INTERIM ANALYSIS METHODOLOGY

Outcomes A, B, D

For these binary outcomes, they will be summarised as the number and proportion of children who had the outcome as yes between F0 and F1 by treatment groups and by clinical outcome groups.

The comparison between treatment groups will be made using a GLM approach with Gaussian error distribution (to avert convergence difficulties with low prevalence outcomes), linear link function and a cluster-robust standard error calculation to account for clustering by study site. The RD and 95% CI will be derived, adjusted by the age group at randomisation (1-5 years; 6-10 years) and SPT wheal size (≤10mm; >10mm).

The RR (with 95% CI) comparing treatments will also be estimated using a GLM approach (the "modified Poisson" approach of Zou, employing the Poisson family, a log link function and a cluster-robust standard error calculation to account for clustering by site), adjusted by the age group at randomisation (1-5 years; 6-10 years) and SPT wheal size (≤10mm; >10mm).

The comparison between clinical outcome groups will be made using a binary regression model. The RD, RR and 95% CIs will be derived.

Outcome C, F, G

For these categorical outcomes, they will be summarised as the number and proportion of children who had the outcome in each category by treatment groups and by clinical outcome groups. They will also be summarised as the median, IQR and range by treatment groups and by clinical outcome groups.

Outcomes C, E, F, G, I

For these continuous outcomes, they will be summarised as mean and SD or median and IQR by treatment groups and by clinical outcome groups as specified.

The mean difference between treatment groups will be obtained by using GLM to account for clustering by site, adjusted by the age group at randomisation (1-5 years; 6-10 years) and SPT wheal size (≤10mm; >10mm). The median difference using quantile regression model to adjust for the stratification factors if not normally distributed.

The mean difference between clinical outcome groups will be obtained by using a linear regression model. The median difference using quantile regression model if not normally distributed. For outcome I, linear/quantile regression model will be used for further adjusted for baseline QoL score.

Outcome H

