We will also compare the QoL scores between treatment groups using a mixed model applied to the data at 4 timepoints (T0, T1, T3/F0, F1) and account for clustering by study site, with fixed effects for treatment, age group at randomisation and SPT wheal size, and a random effect to allow for repeated measures for each individual.

SIGNATURES PAGE

Signature of Group Leader:

[name]

Date 04 -Jun - 2022

Print Name

[name]

Signature of Principal Investigator:

ale

Date 31-May-2022

Print Name

[name]

Signature of Trial Statistician:

Print Name

[name]

Date 10-May-2022

[name]

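### Outcome I: the randomised comparison of QoL change does not list baseline QoL as a covariate, although the clinical-outcome comparison does, and this gives up precision

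*SAP*

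**What the plan says.** Table 1 in SAP Section 4.1 defines outcome I as the change in QoL scores (total, sub-scores and FAIM) "from screening in PPOIT- 003 study to F1". It serves objective 2, which names PPOIT vs OIT vs placebo first and the clinical outcome groups second.

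**Treatment groups.** In Section 5.2, outcome I is handled in one block with C, E, F and G: "The mean difference between treatment groups will be obtained by using GLM to account for clustering by site". The only covariates named for this model are the two stratification factors, age group and SPT wheal size. The skewed-data alternative reads: "The median difference using quantile regression model to adjust for the stratification factors if not normally distributed". Section 5.1 gives the same covariates under its heading on treatment effects between treatment groups. Baseline QoL is not listed in either place.

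**Clinical outcome groups.** Under the separate Section 5.1 heading for these groups the SAP adds: "Adjusted linear regression will be used to adjust for baseline QoL score in outcome I". In Section 5.2 the paragraph on the same groups ends: "For outcome I, linear/quantile regression model will be used for further adjusted for baseline QoL score".

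**Mixed model.** Sections 5.1 and 5.2 (under outcome H) also compare QoL between treatment groups with a mixed model on T0, T1, T3/F0 and F1, "with fixed effects for treatment, age group at randomisation and SPT wheal size", plus a random effect for the individual.

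The SAP gives no reason for treating baseline QoL differently in the two comparisons.

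**The concern.** The screening score must be available for every child who has an outcome I value, since it is subtracted to form that value. Using it as a covariate in the non-randomised comparison while leaving it out of the randomised one discards information at no saving.

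An unadjusted change score fixes the coefficient on baseline at 1, whereas regression adjustment estimates it. Unless the two happen to coincide, the unadjusted contrast has the larger variance. In a small arm it also keeps part of any chance difference in baseline QoL. At stake is the width of the interval that answers objective 2 for the randomised groups, in a follow-up study whose sample size rests on no formal calculation.

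**Working it through.** The SAP states no SD, effect size or power for QoL, so there is no figure of its own to reproduce.

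**Inputs**
- Arm sizes (Section 2.1, Sample size): "PPOIT n=79; OIT n=83; placebo n=39"; 79 + 83 + 39 = 201.
- Expected missing follow-up (Section 5.1): 25%. Applied equally to each arm, which is an assumption, this leaves 79 × 0.75 = 59.25, 83 × 0.75 = 62.25 and 39 × 0.75 = 29.25, or about 59, 62 and 29.
- Correlation r between screening and F1 scores: not in the SAP; range 0.3 to 0.8 assumed.
- Equal SD s at screening and F1: assumed.

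**Formulas for a two-arm mean difference**
- Unadjusted change score: Var = 2s²(1−r)(1/n₁ + 1/n₂)
- Change score adjusted for baseline: Var = s²(1−r²)(1/n₁ + 1/n₂)
- Ratio: (1−r²) / [2(1−r)] = (1+r)/2, whatever the arm sizes

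**Results for PPOIT vs placebo at 59 vs 29**, where √(1/59 + 1/29) = 0.227. Standard errors are in units of s.

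| r | variance ratio | SE unadjusted | SE adjusted | CI narrower by | unadjusted variance is larger by a factor of |
|---|---|---|---|---|---|
| 0.3 | 0.65 | 0.268 | 0.216 | 19% | 1.54 |
| 0.5 | 0.75 | 0.227 | 0.196 | 13% | 1.33 |
| 0.7 | 0.85 | 0.176 | 0.162 | 8% | 1.18 |
| 0.8 | 0.90 | 0.143 | 0.136 | 5% | 1.11 |

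A simulation at 59 vs 29 (5000 runs) gave 0.266 vs 0.219, 0.224 vs 0.198 and 0.175 vs 0.164 at r = 0.3, 0.5 and 0.7. This agrees with the table. Both analyses recovered the true difference on average.

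**Unequal variances.** With SDs s₀ at screening and s₁ at F1, the two variances differ in proportion to (s₀² + s₁² − 2r s₀s₁) − s₁²(1−r²) = (s₀ − r s₁)². This is never negative, so in large samples the direction does not depend on the equal-variance assumption. Only the size does.

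**Chance imbalance.** With equal variances, a baseline difference d between arms shifts the change-score estimate by (1−r)d in magnitude. The standard error of d at 59 vs 29 is 0.227 s. A one-standard-error imbalance therefore shifts the estimate by 0.16, 0.11, 0.07 or 0.05 s at r = 0.3, 0.5, 0.7 or 0.8. Adjustment removes this shift.

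**Mixed model.** With treatment as a main effect and no time or treatment-by-time term, the treatment coefficient averages all four visits, including T0, where no effect can exist. A true effect of −0.50 at each of the three later visits is then estimated as 3/4 × (−0.50) = −0.375. The simulation gave −0.37 to −0.38.

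**The case against.** **The adjustment may already cover both comparisons.** The last outcome I sentence in Section 5.2 names neither comparison. It speaks of further adjustment, and within that block only the treatment-group models have a prior adjustment to build on. This is a fair reading of the sentence alone. Against it, the sentence closes the clinical-outcome paragraph, and Section 5.1 puts the adjustment under the clinical-outcome heading and nowhere under the treatment-group one. The narrower reading is the better one. If the broader one was meant, two analysts could still fit different models from this text, and the same edit cures it.

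**Baseline QoL does enter a randomised analysis.** This stands. A reader might infer that the SAP leaves baseline QoL out of every treatment-group analysis, but the mixed model includes T0. As written, however, that model does not estimate the F1 contrast and cannot take the place of an adjusted analysis of outcome I.

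**The randomised estimate is valid either way.** This also stands. A reader might infer that regression to the mean biases the unadjusted contrast, or that baseline imbalance passes into it in full. Neither follows. Regression to the mean affects randomised arms alike in expectation, and only the fraction (1−r) of an imbalance is carried through. Selective roll-over or non-response is a separate matter that one covariate does not settle.

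**The gain may be small.** If r is high it is, at about 5% of the standard error at r = 0.8. The SAP gives nothing from which to choose r. The figures also ignore age group, SPT and clustering over three sites, and they apply to mean differences, not to medians.

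**Conclusion.** The point holds as a loss of precision, not as a bias. On the better reading of Sections 5.1 and 5.2, the treatment-group analysis of outcome I omits a covariate that is already collected and that the SAP itself uses in the other comparison. The intervals for mean differences would be about 5% to 19% narrower for r between 0.8 and 0.3, assuming equal variances at screening and F1. The figures of 59 and 29 children rest on equal attrition in each arm, but the percentage gain does not depend on them. The change is worth making before the F1 analysis; its absence does not invalidate the comparison. Nothing here argues for dropping the pre-specified median analysis for skewed scores.

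**What to change.** In Sections 5.1 and 5.2, state for outcome I that the treatment-group GLM and the treatment-group quantile regression both include the corresponding PPOIT-003 screening score (total, each sub-score, FAIM) as a continuous covariate, alongside age group, SPT wheal size and the handling of site. Keep the median option as specified. Reword the closing outcome I sentence in Section 5.2 so that it names the comparisons it covers.

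In step 2 of the sensitivity analysis (Section 5.1), add the screening QoL score to the imputation model, which now lists the stratification factors and the T3/F0 and F1 outcomes.

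If the mixed model is also meant to answer objective 2, add time and treatment-by-time terms and report the F1 contrast.

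**Cost:** one degree of freedom and one extra variable in the analysis and imputation code. No new data are needed. No child leaves the available-case analysis, because a child without a screening score has no outcome I.
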